15.1 Potential Risks

Refer to Section 14.1.3 for a list of potential risks.

15.2 Minimization of Risks

This study involves the use of FDA-cleared, Class II medical devices that deliver oxygen therapy with no greater than minimal risk to study patients. All study devices will be used in accordance with their respective approved indications and instructions. The selection of qualified investigators and the provision of study training to site personnel prior to each site's study initiation constitute additional efforts to minimize risk.

In this study, patients will be contacted at 1-week and 6-weeks and will return for a final study visit at 12-weeks post-randomization, allowing for the assessment of adverse events.

15.3 Potential Benefits

Patients may be inclined to increase their physical activity level by participating in this study; however, it is possible that patients will not experience any benefits from study participation. The results of this study may guide the future treatment of patients with COPD.

15.4 Conclusion

The study sponsors firmly believe that the value of the knowledge to be gained by conducting this clinical study to demonstrate the potential of POC devices to positively influence physical activity level in COPD patients outweighs any potential risks posed to participating patients.

16 Study Devices

16.1 Packaging and Labeling

Labeling describing relevant contraindications, hazards, adverse effects, interfering substances or device, warnings, and precautions are provided in the ActiGraph GT9X Link + ActiLife Quick Start Guide, ResMed POC User Manual, and the Inogen POC User Manual. Study devices (POC, ActiGraphs) will be sent to the sites from Sherpa Clinical Packaging. See the eTMF for logistical information on device shipment/returns and Sherpa Clinical Packaging contact information.

16.2 Handling and Storage

The investigator must ensure that all study devices are stored in a secure location until issued to a study patient. All supplies are to be used only for this study and not for any other purpose. The investigator must return all devices to the sponsor(s) at the conclusion of the study.

16.3 Device Accountability

The investigator is responsible for study device accountability, reconciliation and record maintenance. The investigator must maintain study device accountability records throughout the course of the study.

16.4 Device Distribution to/from Patients

Upon being randomized to a study arm, all patients will receive an activity monitor and a diary to record oxygen usage. Patients who are randomized to the treatment arm will also receive the POC device assigned for distribution by his/her specific study site. At the time of device distribution, patients will be informed that they must return all study devices at the end of study participation. Patients are required to return all study devices (POC [if applicable], ActiGraph) to the site at the 12-week visit (or at study termination, if earlier). Sites will return the study devices to Sherpa Clinical Packaging in a bulk shipment at the end of the study. Patients will have the option to purchase their POC device used in the study.

16.5 Device Troubleshooting/Help Desk

Study patients will be provided with contact information for trouble-shooting all study devices (POCs, ActiGraph).

17 Study Administration

17.1 Institutional Review Board (IRB) Approval

The study must be reviewed and approved by the site's IRB before patient enrollment begins at the site. A signed copy of the IRB approval letter and IRB-approved ICF/HIPAA form must be submitted to RCRI. Investigators are responsible for submitting and obtaining initial approval and continuing approval from the IRB and forwarding copies of the approval letters and ICF/HIPAA forms to RCRI. The investigator will notify RCRI within five (5) working days in the event of withdrawal of IRB approval.

17.2 Clinical Trial Agreement and Financial Disclosure

The investigator agrees to be responsible for conducting this study in accordance with the signed clinical trial agreement and this protocol, including study team oversight/management, reporting and record-keeping requirements and controlling the study devices. In addition, the investigator is responsible for ensuring that proper informed consent is obtained from each patient prior to participating in the study as well as protecting the rights, safety and welfare of participating patients.

All investigators will be required to sign a financial disclosure form, which certifies the investigator's and his/her immediate family's financial interest in the study sponsors and study outcomes. Investigators must inform RCRI of any changes related to financial disclosure throughout the course of the study and for a period of two years after the study is terminated.

17.3 Patient Confidentiality

All information and data sent to RCRI, the study sponsors and/or their designees concerning patients and their participation in this study are considered confidential by RCRI, the study sponsors and their designees (subcontractors or contract research organization). Only authorized RCRI and sponsor personnel or approved contracted agents will have access to some portions of these confidential files and will act in accordance with applicable regulations as required by HIPAA. The IRBs also have the right to inspect and copy all records pertinent to this study.

17.4 Patient Compensation

Patients will receive compensation from the sponsors for their participation in the study upon completion of the 12-week visit. Compensation is also contingent upon the return of all study devices and will be provided to the patient by the investigational site. The compensation amount will be specified in the Informed Consent Form and the Clinical Trial Agreement.

17.5 Investigational Site Qualification

Investigational site qualification visits or phone calls will be conducted by RCRI prior to acceptance of a site into this study. As part of the study site selection criteria, investigators will be familiar with the use of POC devices and LTOT. The site qualification visit/call will be scheduled to include time with the investigator, co-investigators, study coordinator and other study personnel. Topics of discussion will include a review of personnel qualifications, investigator qualifications, adequacy of potential patient pool, clinical study experience, study-specific requirements for procedures and equipment, and a review of staffing and equipment availability and appropriateness. A written report of the qualification visit/call will be drafted by RCRI. Resolution of any concerns and/or completion of any necessary activities identified during the visit/call will be documented and submitted to the investigator.

17.6 Site Training

Study-specific training of study personnel is the responsibility of RCRI and the investigator. Study training will occur before first enrollment. To ensure protocol compliance as well as accurate data collection, site training will include a detailed review of the protocol, eCRF completion, study-specific procedures, study devices, and monitoring logistics. Product-specific training will be provided for the POC device to be distributed by the site, the activity monitor (and associated software) and the oxygen diaries during the site initiation visit.

17.7 Data Management

Study-specific eCRFs will be used to enter study data into the EDC system. The PI or designated study personnel at each site is responsible for entering data into the CRFs. Queries/corrections will be managed within the EDC system via electronic queries. Prior to final database lock, the investigator will electronically sign each eCRF; this responsibility cannot be delegated to another person.

Data and eCRFs will be reviewed by study monitors at regular intervals throughout the study as outlined in the study monitoring plan. Data clarification requests (DCFs or queries) may be generated by a monitor during a monitoring visit and/or during remote data review. Data management, including DCFs, will be conducted in accordance with the study's Data Management Plan.

17.8 Investigator Responsibilities

The investigator is responsible for ensuring that the study is conducted according to the Clinical Trial Agreement, the protocol, IRB requirements and HIPAA. Specific responsibilities are listed in the Clinical Trial Agreement and this protocol.

Records and reports must remain on file at the investigational site for a minimum of two years after the completion/termination of this study. They may be discarded only upon written approval from ResMed and Inogen. The investigator must contact ResMed and Inogen before destroying any records and reports pertaining to the study to ensure that they no longer need to be retained. In addition, RCRI must be contacted if the investigator plans to leave the site to ensure that arrangements for a new investigator or records transfer are made prior to investigator departure.

17.8.1 Investigator Records

Records to be maintained by the investigator include:

- Protocol and all amendments
- Signed Clinical Trial Agreement
- Signed Financial Disclosure Forms
- IRB approval letter including consent and HIPAA authorization form(s)
- IRB Membership list or Letter of Assurance
- All correspondence relating to the study between the site and study sponsors and/or RCRI
- CVs and professional licenses for all investigators
- Site personnel signature and responsibility list
- Clinical monitor sign-in log
- Patient screening log
- The following records will be maintained for each patient enrolled in the study:
 - Patient-signed ICFs and HIPAA forms
 - Complete, accurate and current source documentation for CRFs
 - Adverse event reports and any supporting documentation
 - Protocol deviations
 - Complete medical records relative to the study

- Records pertaining to patient death during the study (including death records, death certificate, and autopsy report if performed).

The study sponsors reserve the right to secure data clarification and additional medical documentation on patients enrolled in this study at any time.

17.8.2 Investigator Reports

Investigators are required to prepare and submit reports to their respective IRB in accordance with the IRB's requirements.

17.8.3 Investigational Site Termination

The sponsors reserve the right to terminate an investigational site for any of the following reasons:

- Failure to secure patient informed consent or HIPAA authorization prior to enrollment
- Failure to properly report adverse events
- Repeated protocol violations
- Repeated failure to appropriately complete eCRFs
- Failure to enroll an adequate number of patients
- Loss of or unaccounted for study product inventory
- Administrative decision by the company

17.9 Protocol Amendments

Investigators may not modify this protocol without obtaining written concurrence of RCRI, the sponsors, and the IRB

The purpose of this Statistical Analysis Plan (SAP) is to summarize the statistical methodologies being used to determine the required sample size for and to analyze all endpoints associated with the use of portable oxygen concentrators (POC) combined with standard of care (SOC) long-term oxygen therapy (LTOT) (treatment) versus SOC alone (control) for 12 weeks among subjects prescribed long term oxygen therapy for diagnosed COPD.

2 Early Study Closure

Due to the outbreak of 2019 Novel Coronavirus (COVID-19) in the United States in March 2020, in particular because of the inherent health risks in this for COPD patients on LTOT and the likely negative impact to their Physical Activity Levels (PAL) (i.e., the patient population and primary endpoint for this study, respectively), the decision was made to prematurely terminate the study effective April 30, 2020. At the time of study closure, 109 of the planned 190 subjects (57%) had been enrolled, of which only 3 were still actively participating in the study.

The following impacts of the COVID-19 outbreak from March 2020 through the final study site closure will be summarized in the final report, where applicable:

- A listing of all subjects impacted by COVID-19-related study disruption, including how they were impacted, along with any related analyses and/or discussions as appropriate
- Analyses and corresponding discussions that address the impacts of the implemented contingency measures (e.g., trial participant discontinuation from investigational product and/or study, alternative procedures used to collect critical safety and/or efficacy data) on the safety and efficacy results for the study
- A summary of the reasons for failing to collect any efficacy endpoints, including identifying specific limitation imposed by COVID-19 leading to the inability to perform the protocol-specified assessment

3 Study Design

3.1 Study Design/Overview

This is a post-approval, randomized, unblinded, multicenter, parallel group study with 12 weeks of followup. The study will be performed at up to twenty (20) centers in the United States. Up to 190 subjects (95 per treatment arm) will be enrolled in the study.

3.2 Device Descriptions

3.2.1 SOC Devices for Long-Term Oxygen Therapy

All subjects enrolled in the study will receive ambulatory and non-ambulatory SOC devices for long-term oxygen therapy such as oxygen tanks, transfill devices, and stationary oxygen concentrators.

3.2.2 POC (Investigational) Devices

Subjects randomized to the treatment arm will receive a commercially available POC to provide portable oxygen using pulsed-flow technology. Pulsed-dose oxygen is provided in a pre-programmed bolus amount only as the patient inhales. Each center will distribute either ResMed or Inogen POC devices, both of which have been cleared for market by FDA through the 510(k) process and are to be used in accordance with their respective current indications for use and User Manual/Operator's Manual. For the

purposes of this study, subjects randomized to the control arm may not use a POC device as an ambulatory oxygen option.

3.2.3 ActiGraph GT9X Link

All subjects enrolled in the study will receive an ActiGraph GT9X Link wearable device to collect physical activity data throughout the study. A CentrePoint (CP) data hub is also included with the ActiGraph device to upload the physical activity data.

3.2.4 Oxygen Use Diaries

All subjects enrolled in the study will receive a diary to record oxygen usage throughout the study. All subjects will record daily usage of SOC oxygen and subjects randomized to use a POC will also record daily usage of POC oxygen.

3.3 Study Schedule

3.3.1 Visit 1 (Enrollment/Baseline/Randomization)

Subjects will have an initial visit (Visit 1) to consent to the study, complete all baseline assessments, be randomized to a treatment group, and to receive their study devices (with training) and diaries.

3.3.2 Phone Calls (Week 1 and Week 6)

The centers will call subjects during Week 1 and Week 6 (± 3 days) of the study to asses and record updates on unreported or ongoing adverse events, record updates on respiratory condition-related concomitant medications, assess protocol compliance, address any questions or concerns, and provide additional device training (as needed).

3.3.3 Visit 2 (Week 12 Follow-Up)

Subjects will have a follow-up visit (Visit 2) during Week 12 (± 7 days) of the study to return all study devices and diaries, perform an ActiGraph device data download, complete all follow-up assessments, assess and record updates on unreported or ongoing adverse events, and record updates on respiratory condition-related concomitant medications. Completion of this visit will result in the completion of study participation

3.3.4 Randomization

Subjects will be randomized according to the pre-specified randomization schedule following the confirmation of enrollment eligibility. Subjects will be randomized to either the treatment or control arm in a 1:1 ratio. The randomization will be based on random, permuted blocks and stratified by center. Randomization will continue sequentially regardless of a subject not being treated according to their randomization assignment.

4 Study Objectives

This study is designed to evaluate the effect of using a POC combined with SOC long-term oxygen therapy versus SOC long-term oxygen therapy alone on the physical activity level of subjects with COPD requiring long-term oxygen therapy. This study will also assess the effect on oxygen usage, quality of life, hospitalizations, and death and the safety of the device.

5 Endpoints

5.1 Primary Effectiveness Endpoint

The primary effectiveness endpoint is defined as the change in physical activity level (PAL) from baseline to the week 12 follow-up visit.

5.2 Secondary Endpoints

The secondary endpoints are:

- 1. Average daily oxygen usage
- 2. Quality of life
 - a. St. George's Respiratory Questionnaire
 - b. Hospital Anxiety and Depression Scale
- 3. Six Minute Walk Test (6MWT) distance
- 4. Frequency of COPD exacerbation
- 5. COPD or other respiratory condition-related inpatient hospitalization ≥ 24 hours
- 6. Average number of steps taken per day (non-hospital days)
- 7. Mortality due to COPD or other respiratory condition (primary cause of death)
- 8. All-cause mortality

5.3 Exploratory Endpoints

The exploratory endpoints are:

- 1. Time from enrollment to hospitalization for a COPD or other respiratory condition-related inpatient hospitalization ≥ 24 hours
- 2. Number of days in hospital for COPD or other respiratory condition-related inpatient hospitalization ≥ 24 hours
- All-cause unplanned hospitalizations
- 4. Average daily activity duration and intensity
- 5. Average energy expenditure/day

5.4 Adverse Events

All adverse events will be recorded and reported.

6 Analysis of Primary Effectiveness Endpoint

The primary effectiveness endpoint analysis evaluates the difference in the mean change in PAL from baseline to the week 12 follow-up visit between the treatment and control arms. For accuracy, only wear-filtered ActiGraph data will be used in the analysis. The baseline PAL uses the average TEE and average SEE values during the first week of the study and the week 12 follow-up visit PAL uses the average values from the twelfth week of the study. Only subjects with available baseline and week 12 follow-up visit PAL values will be included in this analysis.

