14.3 Analysis of Secondary and Exploratory Endpoints

The full list of all secondary and exploratory endpoints can be found in Section 5.3. The mean changes from baseline in continuous secondary and other endpoints will be compared between treatment groups via independent samples t-tests, or a non-parametric equivalent as appropriate. General Linear Modeling will be used to assess the impact of potentially influential covariates.

For comparisons of categorical variables, a chi-square test (if appropriate) or Fisher's exact test will be used. Standard logistic regression will also be fit to these endpoints to include center effects and relevant covariates.

For certain variables associated with only one treatment arm, such as POC usage, summaries and estimation, including 95% confidence intervals, may be provided, with no formal hypothesis test performed.

The frequencies of each individual type of adverse event will be summarized along with a 95% exact binomial upper confidence bound. Adverse events, including UADEs, will also be summarized based upon seriousness, severity and relation to the procedure and the device. Individual adverse events will be listed for both groups, including time to event and resolution.

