6.2 Sample Size

The following assumptions were made while determining the required sample size:

- Patients will be assigned to either the treatment or control arm
- The primary analysis is an inequality comparison of the treatment and control arms
- The standard deviation for both arms is 0.22
- A difference ≥ 0.1 is considered clinically significant (i.e., minimal desired detectable difference)
- The difference between the arms is expected to be 0
- Statistical testing will use a two-sided 5% significance level with at least 80% power

At least 154 subjects (77 per treatment arm) are required to analyze the primary effectiveness endpoint with statistical power. To account for up to 20% attrition and other factors, up to 190 subjects (95 per treatment arm) are required to ensure adequate power is maintained for the primary effectiveness endpoint.

7 Analysis of Secondary Endpoints

The secondary endpoints are evaluated at the week 12 follow-up visit and compare the treatment and control arms. Analysis of the secondary endpoints evaluates the following:

- 1. Change in average daily oxygen usage from baseline
- 2. Change in Quality of Life from baseline
 - a. St. George's Respiratory Questionnaire
 - b. Hospital Anxiety and Depression Scale
- 3. Change in Six Minute Walk Test (6MWT) distance from baseline
- 4. Frequency of COPD exacerbation
- 5. COPD or other respiratory condition-related inpatient hospitalization ≥ 24 hours
- 6. Change in average number of steps taken/day (non-hospital days) from baseline
- 7. Mortality due to COPD or other respiratory condition (primary cause of death)
- 8. All-cause mortality

For secondary endpoints 1 and 6, the baseline and week 12 follow-up visit values are the average value during the first and twelfth weeks of the study, respectively. For accuracy, only wake- and wear-filtered ActiGraph data will be used in the analysis.

The assessments used in secondary endpoints 2 and 3 are performed at both the baseline and week 12 follow-up visits.

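### The arm comparisons ignore the centre stratification and the Visit 1 predictors; adjust for them, and add two supportive PAL analyses because the change score subtracts any first-week POC effect in full

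*SAP*

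**What the plan says.** SAP section 6 states that the primary analysis "evaluates the difference in the mean change in PAL from baseline to the week 12 follow-up visit between the treatment and control arms". Section 6.1 sets the null as equal mean change in the two arms. Section 11.6 supplies the default test for continuous variables, a t-test or Wilcoxon rank-sum test, with no covariates. Section 7 treats changes in SGRQ, HADS and 6MWT the same way.

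On the baseline, SAP section 6 says: "The baseline PAL uses the average TEE and average SEE values during the first week of the study". Protocol 10.3, 10.3.2 and 10.3.3 place randomisation, POC distribution and ActiGraph set-up at Visit 1. The first-week value is therefore recorded after randomisation and, in the POC arm, with the POC in hand.

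Covariates appear in three places:
- Protocol 14.3, on secondary and exploratory endpoints, says "General Linear Modeling will be used to assess the impact of potentially influential covariates". It names no covariates, and the SAP does not repeat it.
- SAP section 8 uses arm, centre, age and baseline 6MWT in the exploratory Cox model.
- SAP 11.3 allows an optional pooling regression of the primary endpoint on centre, arm and their interaction.

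SAP 3.3.4 stratifies the randomisation by centre.

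**The concern.** Two separate matters are involved.

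The first is precision. The SAP treats centre, age and 6MWT as useful predictors in one exploratory model and leaves them out of the primary test. For SGRQ, HADS and 6MWT, the Visit 1 value of the same measure is available and is used only through subtraction. Recruitment has ended, so the analysis model is one of the few remaining ways to recover power.

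The second is what the PAL change score measures. Subtracting first-week PAL is the same as regressing week-12 PAL on it with the slope fixed at 1. If the POC already raises activity in week 1, all of that rise is taken out of the estimate. A POC that works at once and keeps working would then show little or no difference in change.

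**Working it through.** **Inputs.** SAP 6.2 gives a difference of 0.1, two-sided 5%, 80% power and "The standard deviation for both arms is 0.22". I read 0.22 as the SD of change, because the calculation is for mean change. Enrolment at closure was 109 (SAP section 2) and planned attrition is 20%. The week-1 to week-12 correlation r, the ratio of the two SDs and the share f of the effect present in week 1 are not in the documents. Ranges for these are assumptions.

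**1. The plan's figure.** The SAP says "At least 154 subjects (77 per treatment arm) are required to analyze the primary effectiveness endpoint". Normal approximation: 2 × (1.960 + 0.842)² × 0.22² / 0.1² = 76 per arm. The noncentral t gives 77 per arm, with power 80.0%, so the figure reproduces. The SE at 77 per arm is 0.22 × √(2/77) = 0.0355.

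**2. Precision for PAL.** Take equal SDs s at the two weeks.
- Change score variance: 2(1 − r)s².
- Residual variance with first-week PAL fitted: (1 − r²)s². The SE ratio to the change score is √((1 + r)/2).
- Week-12 PAL alone: s². The SE ratio is 1/√(2(1 − r)).

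The table shows 77 per arm, a true difference of 0.1 and no first-week effect. The change score has 80% power.

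| r | SE cut, first-week PAL fitted | SE | Power | SE ratio, week 12 alone | Power |
|---|---|---|---|---|---|
| 0.3 | 19% | 0.0286 | 94% | 0.85 | 91% |
| 0.5 | 13% | 0.0307 | 90% | 1.00 | 80% |
| 0.7 | 8% | 0.0327 | 86% | 1.29 | 58% |
| 0.9 | 2.5% | 0.0346 | 82% | 2.24 | 24% |

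**3. First-week effect.** With true week-12 effect D, the change score targets D(1 − f). The model with first-week PAL targets D(1 − bf), where b = r × SD12/SD1 is the slope. Week-12 PAL alone targets D. For D = 0.1, equal SDs and 77 per arm:
- f = 0.25: the change score targets 0.075 (power 56%). The adjusted model targets 0.0875 (81%) at r = 0.5 and 0.0825 (71%) at r = 0.7.
- f = 0.5: the change score targets 0.050 (29%). The adjusted model targets 0.075 (67%) at r = 0.5 and 0.065 (50%) at r = 0.7.

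The adjusted model removes less only if b is below 1, that is, if SD12/SD1 is below 1/r. At r = 0.7 the limit is 1.43. At r = 0.9, an SD ratio of 1.2 gives b = 1.08, and the adjusted model removes more.

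**4. At the achieved size.** 109/2 = 54.5 per arm. If the planning attrition applies, 54.5 × 0.8 = 43.6. Power of the change score for 0.1 is then 55.5%. With first-week PAL fitted it is 74%, 68%, 62% or 58% at the four values of r.

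**5. Cost of fitting centre.** I simulated 109 enrolled, 20% loss, 20 separately fitted centres, blocks of 4 (block size assumed), and centre, age and 6MWT explaining nothing. Power with first-week PAL also fitted is about 60 to 63% at r = 0.5, 56 to 58% at r = 0.7 and 51 to 53% at r = 0.9, depending on how enrolment is spread over centres. For change in PAL on arm, centre, age and 6MWT it is about 50%, against 55.5% unadjusted. With 8 centres it is about 54%.

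**6. Gain from pre-randomisation covariates.** If they explain a share R² of the variance of change, the SE is multiplied by √(1 − R²). For assumed R² of 0.05, 0.10 and 0.20 the SE falls by 2.5%, 5.1% and 10.6%, before the loss in step 5.

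**7. SGRQ, HADS and 6MWT.** The ratio √((1 + r)/2) applies with each measure's own r. If the Visit 1 value precedes POC use, the expected estimate is unchanged and only the SE falls.

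**The case against.** The strongest defence is that nothing here is an error. An unadjusted two-sample test is valid for the stated hypothesis and matches the sample-size calculation. That stands: the loss is of precision, not validity.

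A reader might infer that week-12 PAL adjusted for first-week PAL should replace the primary analysis. The documents do not support that. The stated null is equal mean change. If the POC raised PAL by 0.1 at both weeks, that null would be true, yet the adjusted model would reject it about 35% of the time at r = 0.5 and 15% at r = 0.7 (77 per arm). It tests something else, and it conditions on a value recorded after randomisation. It reduces the dilution but does not cure it.

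A reader might also infer that adjustment always gives a clearly smaller SE and always removes less of the effect. Steps 2, 3 and 5 show that neither is assured. Nor do the documents say that ANCOVA was considered and rejected; they never mention it.

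Protocol 14.3 partly covers the secondary endpoints. The remaining gap is that its covariates are unnamed and the SAP drops the plan.

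One caution on SGRQ and HADS: SAP 3.3.1 lists baseline assessments before randomisation, but Protocol section 3 lists the Visit 1 assessments after it. Only the 6MWT is explicitly required first (Protocol 10.3).

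**Conclusion.** The point holds as a worthwhile improvement. The case is clearest for SGRQ, HADS and 6MWT, where the Visit 1 value is a natural covariate and adjustment leaves the target unchanged. For the primary endpoint, adjusting change in PAL for centre, age and 6MWT respects the stratified design and keeps the hypothesis. Its gain depends on an R² that the documents do not give, and it can be a small loss if many small centres are fitted separately.

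The dilution by a first-week effect is exact in form: the change score subtracts all of it. Its size is unknown, because no document says how quickly the POC acts. The 19% to 2.5% SE reduction from fitting first-week PAL rests on equal SDs, a change SD of 0.22 and r between 0.3 and 0.9, and excludes the cost of centre. This supports using that model as a supportive analysis, not as the primary one.

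**What to change.** 1. **SGRQ, HADS, 6MWT:** analyse the week-12 value by ANCOVA on arm, centre and the Visit 1 value of the same measure. This carries the modelling in Protocol 14.3 into the SAP with named covariates. Confirm that SGRQ and HADS were completed before randomisation.
2. **Primary:** keep change in PAL. Estimate the arm difference in a linear model with centre, age and Visit 1 6MWT, and report the unadjusted t-test alongside. Combine small centres by a stated rule; Protocol 14.4 already allows for super-centres.
3. **Supportive, prespecified:** (a) week-12 PAL on arm, centre, age and 6MWT, which uses nothing recorded after randomisation; (b) the same model with first-week PAL added and its slope estimated. State that (b) conditions on a post-randomisation value.

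The cost is SAP wording and a few regressions on data already collected. The drawbacks are a somewhat longer report, low precision of (a) when r is high, and the difficulty of interpreting (b). SAP version 1.0 is dated 18 August 2020, after the unblinded trial closed on 30 April 2020. The change must therefore be fixed and dated before arm-level results are examined.
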